### **Statistical power and analysis**

**Statistical power.** Differences in weight loss at six mos. between participants randomized to the IP or EUC, and GP or IP are of primary interest. We hypothesize that six month weight loss will average 2 kg, 8 kg, and 12 kg in the EUC, IP, and GP arms, respectively, with a common standard deviation for weight change of 7 kg (34) (35). Statistical power was determined assuming a type 1 error rate of 2.5% for each of our two primary comparisons. Based on these assumptions, randomization of 200 participants with a 2:2:1 allocation; GP (n=80), IP (n=80), EUC (n=40) will provide 98% power to detect significantly greater weight loss in IP versus EUC, and 91% power to detect significantly greater weight loss in GP versus IP. The global F-test for a one-way ANOVA provides greater than 99% power under these assumptions. The primary analysis will be intent-to-treat with imputation of missing data using multiple imputation techniques. However, a completers only analysis, with a 20% loss to follow-up, will still provide 95% power for the IP-EUC, and 83% power for the GP-IP comparisons.

**Analysis plan.** A global one-way ANOVA will be followed with two pairwise t-tests on the two comparisons of interest, IP versus EUC, and GP versus IP. Statistical significance for each pairwise comparisons will be  $p \leq 0.025$ ; however, all other analyses will be conducted at  $p < 0.05$ . These primary analyses will be intent-to-treat utilizing multiple imputation for missing data and to determine corresponding  $p$ -values. In addition to the intent-to-treat analysis, a completers only analysis will be performed, i.e., participants with weight at 6 months. Secondarily, we will compare weight between the three study arms across 24 months using a mixed linear model,

assuming an autoregressive correlation structure of weight over time, controlling for baseline weight, treatment group and time as covariates. The global comparison across the three arms will be followed by two pairwise comparisons of interest, i.e., IP versus EUC, and GP versus IP. Independent comparisons of change in each chronic disease risk factor, i.e., waist circumference, triglycerides, HDL cholesterol, blood pressure, and fasting glucose at 6, 12, and 18 mos., across the 3 intervention arms will be completed using a mixed linear model, assuming an autoregressive correlations structure. We will also compare Quality of life (SF-36), daily stress associated with eating (Nutrition Hassles Questionnaire), self-efficacy for weight change (WELS), self-efficacy for exercise (EXES), and self-efficacy for overcoming barriers to exercise (BARSE) among the three intervention arms across 24 months using a using a mixed linear model assuming an autoregressive correlation structure both unadjusted and adjusted for covariates. A variety of exploratory analyses, as deemed appropriate by the principal investigator and the project biostatistician, e.g., assessment of the impact of health educator absences and turnover, community environment for healthy eating and PA etc. on weight loss outcomes, will be performed. Analyses will be completed using SAS version 9.4 or higher.

**Missing data.** We will determine if the proportion of participants lost to follow-up differs by intervention arm and/or sex, and compare demographic characteristics between those lost to follow-up and completers. If there are differences across treatment groups, we will examine demographic characteristics, i.e., sex, age, magnitude of weight loss, between completers and those lost to follow-up, to determine if there are significant differences ( $p < 0.05$ ) in those characteristics. If missing data are related to intervention group and/or demographic characteristics, we will use model based multiple imputation; otherwise, traditional multiple imputation will be used.

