**Group phone intervention: Delivery/session content.** The GP intervention will be delivered to 12-15 participants during a 45 minute call weekly from 0-6 mos. and biweekly from 7-18 mos. using the MaestroConference® software platform (Oakland, CA) that allows group audio conferences to be accessed by phone. Approximately five minutes prior to scheduled meetings, typically late afternoon or early evening, participants will call a toll-free line and enter a unique code number to join the meeting. Participants will be required to remain on the call for the duration of each session to be considered as having attended the session. Call duration for each participant is monitored by the Maestro software. Each meeting will include a check-in question to generate discussion regarding diet and PA, a review of participants self-monitored diet, weight and PA data reported since the previous meeting, a lesson on a weight management topic, and an experiential learning assignment requiring problem solving, or the practice of behavioral strategies, to be completed prior to the next meeting. Sample topics include: energy density (increase volume, not calories), obtaining fruits and vegetables in rural communities, exercising in rural communities, eating/exercising on the go, etc. Several sessions at the end of the weight loss phase (mo. 6) will include discussions regarding complying with a conventional diet, i.e., meal planning, food shopping, meal preparation, portion control, etc. During weight maintenance (7-18 mos.) group sessions will focus on planning and following a meal plan diet with or without incorporation of portion controlled entrées/shakes, and cardinal behaviors for successful weight maintenance such as self-monitoring, regular PA, eating on weekends/vacations, and controlling EI on special occasions and holidays, etc.

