**Individual phone intervention: Delivery/session content.** The IP intervention will be delivered via brief, i.e., ~15 min. scheduled phone calls weekly from 0-6 mos. and biweekly from 7-18 mos.. Prior to each call participants will be asked to read a lesson in the study notebook. Lesson topics will parallel those in the GP intervention and focus on weight loss over mos. 0-6 and weight maintenance during mos. 7-18. During each call, health educators will highlight the major points of the lesson, review self-monitoring data relative to weight, diet and PA, and problem solve, if necessary. Thus, the IP intervention is predominately self-directed with minimal education and support from the health educator. In contrast, the GP intervention includes health educator directed, 45 min educational/behavioral sessions, and provides both health educator and group support.

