**Cost analysis.** Differences in total costs and cost effectiveness; i.e., cost/kg weight loss between intervention arms will be evaluated using a one-way analysis of variance (ANOVA). We will also make qualitative comparison between the cost effectiveness of our interventions and others reported in the literature, such as the Diabetes Prevention Program (93). Weight loss represents only one potential benefit associated with participation in a weight management program. Other potential benefits included improved health, enhanced attractiveness, increased vitality and productivity etc. We will use contingent evaluation analysis where participants express preferences for hypothetical programs with different attributes such as costs, time, delivery method, and magnitude of weight loss to determine how differences in these affect preferences for the GP, IP and enhanced usual weight management strategies. Contingent valuation data will be analyzed using conditional logit analysis, with adjustments for clustering of observations within clinics.

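### The GP versus IP t-test and its stated 91% power treat group-phone participants as independent, although they are treated in interactive call groups of 12-15; the 2.5% error rises with call-group correlation, to about 5% at an assumed ICC of 0.05

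*Combined protocol and SAP*

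**What the plan says.** The Analysis plan paragraph of Statistical power and analysis sets the primary analysis: "A global one-way ANOVA will be followed with two pairwise t-tests on the two comparisons of interest, IP versus EUC, and GP versus IP". Each pairwise test is judged at 0.025. The Statistical power paragraph claims "91% power to detect significantly greater weight loss in GP versus IP" for 80 per arm, and 83% among completers if 20% are lost. On missing weights it adds: "These primary analyses will be intent-to-treat utilizing multiple imputation for missing data".

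Delivery differs between the two arms. Under Group phone intervention: Delivery/session content, "The GP intervention will be delivered to 12-15 participants during a 45 minute call weekly from 0-6 mos". The IP arm receives short one-to-one calls. The IP section contrasts the two formats and says that GP "provides both health educator and group support". The Introduction likewise presents interaction among participants as an advantage of the group format.

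No weight analysis mentions call groups. The secondary weight model is described as "assuming an autoregressive correlation structure of weight over time, controlling for baseline weight, treatment group and time as covariates", which is correlation over time within a person. The Missing data paragraph says: "If missing data are related to intervention group and/or demographic characteristics, we will use model based multiple imputation"; there the intervention group is the trial arm. Clustering is addressed once, by clinic and for another outcome: "Contingent valuation data will be analyzed using conditional logit analysis, with adjustments for clustering of observations within clinics".

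**The concern.** People who share a weekly call for six months, with the same discussion and peer support, may have more similar weight changes than people in different calls. The protocol gives its own reason to expect this, and it applies to GP only. If the correlation is positive, the GP mean varies more from trial to trial than a t-test on 80 independent people assumes. The test then rejects a true null more often than declared, and an interval built on the same standard error would be too short.

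GP versus IP is one of two primary comparisons, and splitting the error into two parts of 2.5% is the plan's multiplicity control. The stated power also has an unstated condition, that call-group correlation is zero.

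**Working it through.** **Inputs from the plan** (Statistical power; Group phone intervention; Clinic recruitment): expected losses of 12 kg (GP), 8 kg (IP) and 2 kg (EUC), so 4 kg for GP versus IP; SD 7 kg; arms of 80, 80 and 40; error 0.025 per comparison; calls of 12-15; about 40 recruits per clinic.

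**Assumptions, not in the documents:** ICCs of 0.01, 0.02, 0.05 and 0.10, and the number of call groups. For 80 people in calls of 12-15, five groups hold at most 75, six hold 72-90, and seven need at least 84, so six is the only count that fits. One group in each of five clinics would have 16 members (80/5), just outside the range. Both layouts are shown.

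**1. The plan's own figures.** Standard error = 7 × √(2/80) = 1.107 kg; 4/1.107 = 3.61. The noncentral t with 158 df, two-sided 0.025, gives 91.0%. With 64 per arm, the standard error is 7 × √(2/64) = 1.237, 4/1.237 = 3.23, and power is 83.1%. Both match the plan, and both treat every participant as independent.

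**2. Error of the planned t-test.** For group size m, the GP design effect is D = 1 + (m − 1) × ICC; for IP it is 1. The true variance of the difference is R = (D + 1)/2 times what the t-test assumes. Actual error is about 2 × [1 − Φ(2.2414/√R)]. Six groups (m = 80/6 = 13.33) at ICC 0.05: D = 1 + 12.33 × 0.05 = 1.617; R = 1.308; √R = 1.144; 2.2414/1.144 = 1.96; error 5.0%.

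| ICC | √R, six groups | Error: formula / simulated | √R, five groups of 16 | Error: formula |
|---|---|---|---|---|
| 0 | 1.00 | 2.5% / 2.5% | 1.00 | 2.5% |
| 0.01 | 1.03 | 3.0% / 3.0% | 1.04 | 3.1% |
| 0.02 | 1.06 | 3.4% / 3.5% | 1.07 | 3.7% |
| 0.05 | 1.14 | 5.0% / 5.0% | 1.17 | 5.6% |
| 0.10 | 1.27 | 7.8% / 7.7% | 1.32 | 9.0% |

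These are for complete data and a t-test not conditional on the ANOVA.

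**3. Features of the plan that change the figures** (simulated).
- *ANOVA as a strict gate.* At ICC 0.05 with six groups, error is about 4.1-4.2% when all three arms are equal. If EUC loses 6 kg less than IP, as hypothesized, it is back to 5.0%.
- *Clinic effect shared by the arms* (assumed clinic ICC 0.02-0.05, six groups). Error is 2.2-2.4% with no group effect, and 2.7-2.8%, 3.1-3.3%, 4.7-4.9% and 7.5-7.7% at the four call-group ICCs.
- *Imputation by arm only, 20% random loss.* Error is 2.7%, 3.0%, 4.4% and 6.5% with six groups; 3.0%, 3.3%, 4.9% and 7.4% with five.

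**4. Power when call group is allowed for** (six groups, no clinic term, complete data). The variance of the GP mean is 49D/80 on 5 df, and of the IP mean 49/80 on 79 df, with Satterthwaite df for the difference. At ICC 0.05: 49 × 1.617/80 = 0.990; 49/80 = 0.6125; standard error = √1.603 = 1.266; df = 1.603²/(0.990²/5 + 0.6125²/79) = 12.8; power 73%. The same steps at ICC 0, 0.02 and 0.10 give 87%, 81% and 60%. A simulated mixed model with the group variance bounded at zero gives 85%, 80%, 72% and 60% at ICC 0, 0.02, 0.05 and 0.10.

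**The case against.** The case for the plan has real substance.

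- **No ICC is documented, and 0.05 is only an assumption.** This stands. At 0.01-0.02 the excess is small. However, a single power figure of 91% is itself an ICC assumption, namely zero, and the plan does not say so.
- **One educator per clinic delivers all arms, randomization is within clinic, and fidelity is monitored.** This balances clinic and educator effects and limits differences in delivery. It does not remove correlation arising among people on the same call.
- **The ANOVA may act as a gate, and a shared clinic effect makes the t-test slightly conservative.** Both stand. A reader might infer that the 2.5% holds only if the correlation is exactly zero. That is too strong: either feature leaves some room above zero. But the plan does not say that the ANOVA is a strict gate, and a gate gives no protection under the EUC difference that the plan expects.
- **The model that allows for call group is not exact either.** With the group variance bounded at zero (six groups, no clinic term), its error is 1.7-2.8% over ICC 0 to 0.10. It also costs power even at ICC 0. This argues against insisting that it be primary.

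A reader might also infer that six call groups require a sixth clinic or a group spanning clinics. The documents do not support that: recruitment may be unequal, so one clinic could host two groups. The number of groups is simply not stated.

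**Conclusion.** The point stands in conditional form. That call groups are missing from the primary test, the power calculation, the secondary models and the imputation rules is certain; the size of the effect is not. For the ungated t-test, error at an assumed ICC of 0.05 is about 5.0% (six groups) or 5.6% (five groups of 16) on complete data, and about 4.4-4.9% after arm-only imputation with 20% loss. Error is close to 3% at an ICC of 0.01.

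It would be going too far to conclude that the trial's error rate is 5%, or that the planned test lacks power. The planned t-test still rejects about 85-90% of the time at 4 kg over these ICCs. The issue is error control, and power figures that hold only at ICC 0. IP versus EUC is not affected, because neither arm uses call groups.

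**What to change.** 1. Record a call-group ID for each GP participant, and state how call groups are formed, including whether each sits within one clinic. Without the ID the correlation cannot be estimated.
2. Pre-specify for GP versus IP, at minimum as a sensitivity analysis, a partially nested linear mixed model of 6-month weight change: a random call-group effect in the GP arm only, Satterthwaite or Kenward-Roger df, fitted to observed weights. Report the estimated ICC, and state whether the group variance is bounded at zero.
3. In Statistical power and analysis, state that 2.5%, 91% and 83% assume a call-group ICC of 0. Add GP versus IP power over a range that includes 0; for six groups, no clinic term and complete data, about 85-87% at 0, 80-81% at 0.02, 72-73% at 0.05 and 60% at 0.10.

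Three further choices belong to the sponsor because they cost power: making the nested model primary, adding clinic to it, and putting call group into the imputation model. With clinic in the model and one group per clinic, power at ICC 0 on complete data is about 76% (six groups) or 72% (five). With 20% loss, five clinics and ICC 0, it is about 62% fitted to observed weights and about 50% after imputation with a random call-group term, against about 82% for the planned t-test after arm-only imputation.

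The cost of items 1 to 3 is one recorded field, one extra analysis and a less favourable power statement. No added enrolment is needed.

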## **Methods and Materials**

### **Study Overview**

Health care providers at five primary care clinics, or community health professionals serving individuals in rural Kansas, will be trained to deliver the GP and IP interventions and an

enhanced version of usual care to compare weight loss (0-6 mos.), weight maintenance (7-18 mos.), and weight change during a 6 mo. period of no contact (19-24 mos.) between interventions. The GP and IP interventions will be identical with the exception of the format (group vs. individual) and duration of contact, i.e., GP (~45 min/session) vs. IP (~15 min/session). Usual care, which is generally limited to brief counseling (5-7 min.) during a routine physician visit and/or referral to a registered dietitian (40), will be enhanced by increased contact with the health care providers and provision of information regarding community assets for increased PA and improved nutrition. We considered using an established weight management intervention such as the Diabetes Prevention Program or Look AHEAD protocols (41-43) as a comparison group. Although efficacious in some settings, the delivery of these interventions is expensive and burdensome for both participants and providers, and are unlikely to be tolerated by rural clinics. Following considerable discussion, we decided to compare our GP and IP interventions to an enhanced version of weight management as currently practiced in rural primary care clinics (40), i.e., enhanced usual care (EUC). Two hundred overweight/obese adults will be randomized in a 2:2:1 allocation to the GP (n=80), IP (n=80), or EUC (n=40) arms. Outcomes will be assessed by the research team at baseline (0 mos.), following weight loss (6 mos.), during weight maintenance (12 and 18 mos.) and after a 6 mo. no-contact period (24 mos.). The primary aim is to compare weight change at 6 mos. between the 3 interventions arms; GP, IP, and EUC, analyzed using intention-to treat principles. Secondarily, we will compare the following across the three interventions groups: 1) weight at 12, 18 and 24 mos. 2) metabolic syndrome risk factors (waist circumference, triglycerides, HDL-cholesterol, blood pressure, fasting glucose) at 6, 12 and 18 mos. Cost, cost effectiveness, and contingent valuation analysis and extensive process evaluation will also be completed. Approval for this study has been obtained from the Human Subjects Committee at the University of Kansas-Lawrence.

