### **Clinic recruitment**

At least five clinics, located in rural areas, and/or serving primarily rural residents, with a census of ~4,000 to 8,000 patients will be asked to participate. A universally recognized classification scheme or definition for urban/rural areas does not exist (44-46). For this project we will use the U.S. Census Bureau definition which states: “Rural is defined as all population, housing, and territory not included within an urbanized area or urban cluster” (47). An urbanized area is defined as a population of 50,000 or more, and urban clusters are areas with populations of at least 2,500, but less than 50,000. Each clinic will be asked to assist with recruitment of 40 participants, deliver the interventions and provide space for both outcome assessments and delivery of the EUC intervention arm.

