### **Recruitment/randomization**

In addition to recruitment by rural clinic personnel, we will also recruit using flyers posted in rural communities and media advertising including print, radio and Facebook®. We will recruit at least 50% females and minorities to reflect or exceed minority representation in rural Kansas (16.7%) (49). Potential participants will be asked to contact study staff via phone, email or our laboratory web site. Interested individuals will be directed to complete a brief web-based screener on our laboratory website, or will be interviewed by phone, to assess self-reported height and weight (BMI), medication use, presence of chronic disease, smoking habits, previous attempts at weight loss, and current level of PA. Those satisfying the initial eligibility criteria will be scheduled to attend an in-person meeting with study staff at the participant's respective clinic. At this session staff will describe the project, answer questions, obtain consent, complete eligibility screening surveys, and measure height and weight to determine preliminary eligibility based on BMI. Screening surveys including health history, depression, eating behavior and binge eating will be administered using web-based software (Research Electronic Data Capture software (REDCap), Vanderbilt University, Nashville, TN) (50). These surveys will be completed during the in-person meeting or at home, depending on the availability of home internet access. Project staff will then send a form (fax/email) to the potential participant's primary care physician describing the study and requesting clearance for participation. Final eligibility based on BMI will be confirmed at baseline testing, using height and fasting weight assessed with participants wearing hospital gowns. Participants in each clinic will be randomized, stratified by sex, to one of the three study arms. The randomization sequence will be generated by an independent statistician, sent to the project coordinator and concealed until intervention groups are assigned.

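### The primary ANOVA and t-tests ignore clinic, sex and baseline weight; adjusting would gain modest GP-IP precision if these predict weight change (R² above about 0.03 if arms are not balanced within strata)

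*Combined protocol and SAP*

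**What the plan says.** **Design.** Under Recruitment/randomization: "Participants in each clinic will be randomized, stratified by sex, to one of the three study arms". The same section has baseline weight measured before entry: "Final eligibility based on BMI will be confirmed at baseline testing, using height and fasting weight assessed with participants wearing hospital gowns". Clinic recruitment sets a minimum number of sites, not a fixed one: "At least five clinics, located in rural areas, and/or serving primarily rural residents", with 40 participants sought from each.

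**Primary outcome.** Study Overview: "The primary aim is to compare weight change at 6 mos. between the 3 interventions arms".

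**Primary analysis.** Statistical power and analysis: "A global one-way ANOVA will be followed with two pairwise t-tests on the two comparisons of interest", namely IP versus EUC and GP versus IP, each at 0.025. No covariate is named. On missing data: "The primary analysis will be intent-to-treat with imputation of missing data using multiple imputation techniques". The variables in the imputation model are not listed.

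**Where the three factors do appear.** The secondary weight model over 24 months is fitted "controlling for baseline weight, treatment group and time as covariates", without clinic or sex. Clinic is accounted for only in the contingent valuation analysis (Cost analysis). Sex comes up only in the loss-to-follow-up checks (Missing data).

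**The concern.** Two factors are important enough to stratify the randomisation, and a third is used as a covariate in the secondary weight model, yet the primary comparison uses none of them. A change score subtracts baseline weight; it does not model any relation between baseline weight and the amount lost.

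Two things follow if the factors predict weight change. First, variance that could be explained stays in the error term, so precision is lost. Second, if arms are balanced within clinic-by-sex strata, the between-stratum variation cannot contribute to the arm difference but still enters the unadjusted standard error, which is then too large.

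GP versus IP has most at stake. It has the smaller assumed difference (4 kg against 6 kg) and the lower stated power: 91% with full data and 83% for completers after 20% loss.

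**Working it through.** **Inputs from Statistical power.** Mean losses of 2, 8 and 12 kg (EUC, IP, GP), so differences of 6 kg (IP-EUC) and 4 kg (GP-IP); SD 7 kg; 2.5% error per comparison; n = 80 GP, 80 IP, 40 EUC; 20% loss leaves 64, 64, 32.

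**Assumed.** R² of clinic, sex and baseline weight with 6-month weight change: 0.02, 0.05, 0.10. The documents give no value.

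**Step 1: reproduce the plan.** SE = SD × √(1/n₁ + 1/n₂); power from the noncentral t with noncentrality difference/SE, two-sided 0.025.
- GP-IP: SE = 7 × √(2/80) = 1.107; 4/1.107 = 3.61; critical t (158 df) 2.263; power 91.0%. Stated: 91%.
- IP-EUC: SE = 7 × √(1/80 + 1/40) = 1.356; 6/1.356 = 4.43; power 98.4%. Stated: 98%.
- Completers: GP-IP 83.1%, IP-EUC 95.2%. Stated: 83% and 95%.

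One-sided 0.025 would give 94.9% for GP-IP, so the plan's figures are two-sided and unadjusted.

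**Step 2: formula power with adjustment.** Replace SD by 7 × √(1 − R²). For GP-IP at R² 0.10: SD = 6.641, SE = 1.050, 4/1.050 = 3.81.

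| Power (%) at R² | 0 | 0.02 | 0.05 | 0.10 |
|---|---|---|---|---|
| GP-IP, 80 v 80 | 91.0 | 91.6 | 92.5 | 93.8 |
| GP-IP, completers | 83.1 | 83.9 | 85.1 | 87.1 |
| IP-EUC, 80 v 40 | 98.4 | 98.5 | 98.8 | 99.1 |
| IP-EUC, completers | 95.2 | 95.6 | 96.1 | 97.0 |

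**Step 3: cost in degrees of freedom.** Five clinics (4) + sex (1) + baseline weight (1) = 6. Residual df in the three-arm model falls from 197 to 191 and the critical t moves from 2.2587 to 2.2592, about 0.01 point of power.

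**Step 4: cost of chance imbalance.** The formula assumes covariates balanced across arms. Without balance, estimating 6 covariates inflates the variance of the contrast by roughly 6/200 = 0.03, so R² must exceed about 0.03 to pay.

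Simulation (40,000 trials per scenario; 5 clinics × 40, half of each sex; R² split half to baseline weight and half to clinic and sex; no call-group effect) gives GP-IP power, unadjusted v adjusted (%):

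| R² | Exact 8:8:4 within strata | No blocking |
|---|---|---|
| 0 | 90.9 v 90.7 | 90.7 v 89.9 |
| 0.02 | 91.2 v 91.6 | 90.6 v 90.5 |
| 0.05 | 91.6 v 92.6 | 90.8 v 91.4 |
| 0.10 | 91.8 v 94.0 | 90.8 v 93.0 |

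**Step 5: type I error (nominal 2.5%).** At R² 0.10 the strata carry 0.05. With exact balance the true SE of the unadjusted GP-IP difference is about 1.107 × √0.95 = 1.079 against about 1.107 reported. The test in effect uses 2.263/√0.95 = 2.32, a two-sided level near 2.15%. Simulation gives 2.1% (GP-IP) and 2.2% (IP-EUC). Without blocking it gives 2.5% and 2.6%. The adjusted model stays at 2.4 to 2.7% throughout.

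**Step 6: imputation.** 12,000 trials, exact balance within strata, 20% of 6-month weights missing completely at random (assumed), 50 imputations. With arm only in the imputation model, unadjusted GP-IP power is 82.9% at R² 0 and 83.6% at 0.10, no better than completers. At R² 0.10, covariates in the imputation model alone give 83.9%; covariates in both imputation and analysis give 86.4%.

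**The case against.** **This is a preference, not a defect.** The unadjusted tests match their own power calculation, both contrasts keep more than 80% power after 20% loss, and stratified randomisation with one educator delivering all arms in a clinic already guards against imbalance by clinic and sex. This stands as far as validity goes. A reader might infer that ignoring the strata inflates type I error; it does not. With balance the test is slightly conservative, and without balance it is at its nominal level.

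**The gain depends on an unknown R².** This also stands. A reader might infer that adjustment can only help because 6 of 197 degrees of freedom is so little. The degrees of freedom are indeed nearly free, but chance imbalance is not: unblocked, R² 0.02 yields nothing and R² 0 loses power. Recruitment/randomization does not say how balance within strata is achieved, so the exact-balance column is an ideal case.

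**Imputation may recover the power lost to dropout.** A reader might infer from Step 6 that the planned imputation recovers nothing. The documents do not support that, because the imputation variables are unspecified. GP and IP participants report weight twice weekly, and weight is measured again at 12 and 18 months. If such data existed for every missing case and correlated 0.5, 0.7 or 0.8 with 6-month change (assumed), unadjusted GP-IP power would be about 85.2, 87.1 or 88.3%. That is an optimistic bound, since dropouts may stop reporting.

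**The secondary model already adjusts for baseline weight.** It does and it repeats both contrasts, but across 24 months and not as the primary 6-month test.

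**Call groups matter more.** "The GP intervention will be delivered to 12-15 participants during a 45 minute call weekly from 0-6 mos", so outcomes may cluster by call. With one call group per clinic, exact balance and R² 0.10, GP-IP type I error at an assumed intraclass correlation of 0.05 is 5.3% unadjusted and 6.1% adjusted; at 0.02, 3.6% and 3.8%. This stands as a separate issue that these covariates do not fix. The power figures above assume no such clustering.

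**Conclusion.** The point holds as a modest, conditional improvement in efficiency. The planned primary tests are valid, and the stated powers are correct for an unadjusted analysis without clustering.

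If clinic, sex and baseline weight together explain 5 to 10% of the variance in weight change, formula GP-IP power improves by about 1.5 to 3 points with full data and 2 to 4 points for completers. IP-EUC gains less than 1 point with full data and under 2 points for completers. With arms balanced within strata, the cost when the covariates predict nothing is negligible (0.2 points in simulation), and the unadjusted test runs slightly below its nominal level (about 2.1% at R² 0.10). Without such balance, break-even is at R² of about 0.03 and the worst case is a loss of up to about 1 point.

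The size rests on the assumed R², which nothing in the documents settles. Whether multiple imputation would restore power lost to dropout is open until its variables are specified; with arm alone it would not.

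**What to change.** In the Analysis plan, before outcome data are seen:
- make the primary analysis a linear model of 6-month weight change on arm, baseline weight, sex and clinic;
- take the global arm test and the IP-EUC and GP-IP contrasts from that model, each contrast at 0.025;
- include the same covariates in the imputation model;
- keep the one-way ANOVA and unadjusted t-tests as a sensitivity analysis.

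Cost: wording only, with no new data or participants. The model uses 6 degrees of freedom with five clinics and one more for each extra clinic. The downside is at most about 1 point of GP-IP power if the covariates turn out not to be prognostic. Clustering by GP call group needs its own provision.

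### Fixed 0.025 tests for the two primary comparisons are valid, but Holm would raise GP–IP power from 91% to about 95% at the same 5% family-wise error

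*Combined protocol and SAP*

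**What the plan says.** All of this is in the combined protocol and SAP, section Statistical power and analysis.

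- **Power paragraph:** "Statistical power was determined assuming a type 1 error rate of 2.5% for each of our two primary comparisons". The stated powers are 98% for IP–EUC and, for the other comparison, "91% power to detect significantly greater weight loss in GP versus IP". With 20% loss, the completers analysis is given 95% and 83%. The global F-test is given more than 99%.
- **Analysis plan, sequence:** "A global one-way ANOVA will be followed with two pairwise t-tests on the two comparisons of interest, IP versus EUC, and GP versus IP".
- **Analysis plan, threshold:** "Statistical significance for each pairwise comparisons will be" p ≤ 0.025. Everything else is tested at 0.05.

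No step-down, closed or hierarchical rule is described. The text does not say whether a significant ANOVA is required before the t-tests count.

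**The concern.** Halving alpha protects against the case where both null hypotheses are true. Once one effect is real, only one true null remains, and the fixed rule tests it at 2.5%, leaving half of the 5% budget unused. The plan expects to be in that situation, since it gives IP–EUC 98% power.

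The cost falls mainly on GP versus IP. That is the weaker-powered of the two comparisons, and the Introduction presents the comparative effectiveness of the two phone formats, when delivered by clinic personnel, as the focus of the trial. A step-down rule recovers the unused error rate without adding participants.

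**Working it through.** **Inputs (Statistical power paragraph).** Mean losses: "six month weight loss will average 2 kg, 8 kg, and 12 kg in the EUC, IP, and GP arms, respectively", so IP–EUC is 6 kg and GP–IP is 4 kg. Spread: "with a common standard deviation for weight change of 7 kg". Sizes: GP 80, IP 80, EUC 40; with 20% loss 64, 64, 32. Alpha is 0.025 per comparison. Sidedness is not stated. Two-sided tests reproduce the plan's figures; one-sided 0.025 would give about 95% for GP–IP and does not.

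**Step 1. Reproduce the plan.** SE = SD × √(1/n₁ + 1/n₂), noncentrality = difference / SE, power from the noncentral t with n₁ + n₂ − 2 degrees of freedom.

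| Comparison | SE (kg) | Noncentrality | Critical t, 0.025 | Power | Stated |
|---|---|---|---|---|---|
| GP–IP, 80/80 | 7√(2/80) = 1.107 | 4/1.107 = 3.61 | 2.263 | 91.0% | 91% |
| IP–EUC, 80/40 | 7√(1/80 + 1/40) = 1.356 | 6/1.356 = 4.43 | 2.270 | 98.4% | 98% |
| GP–IP, 64/64 | 7√(2/64) = 1.237 | 4/1.237 = 3.23 | 2.269 | 83.1% | 83% |
| IP–EUC, 64/32 | 7√(1/64 + 1/32) = 1.516 | 6/1.516 = 3.96 | 2.278 | 95.2% | 95% |

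The global F-test exceeds 99.99%. All stated figures reproduce.

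**Step 2. What Holm adds.** GP–IP is rejected if its p ≤ 0.025, or if its p ≤ 0.05 and IP–EUC has p ≤ 0.025. So Holm power lies between the power at 0.025 and the power at 0.05. For GP–IP at 80/80, the power at 0.05 (critical t 1.975) is 94.9%. Because IP–EUC nearly always succeeds under the planning means, Holm comes close to that ceiling.

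**Step 3. Simulation** of three arms with the shared IP arm, 1,000,000 trials per scenario:

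| Planning means | Fixed 0.025 | Holm |
|---|---|---|
| GP–IP, full sample | 91.1% | 94.9% |
| IP–EUC, full sample | 98.4% | 99.2% |
| Both, full sample | 89.4% | 94.1% |
| GP–IP, 20% loss | 83.0% | 89.3% |
| IP–EUC, 20% loss | 95.2% | 97.4% |
| Both, 20% loss | 78.4% | 86.9% |

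**Step 4. Dependence on IP–EUC** (full sample, GP–IP held at 4 kg; the smaller IP–EUC values are assumptions for illustration):

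| True IP–EUC | Fixed 0.025, GP–IP power | Holm, GP–IP power |
|---|---|---|
| 6 kg (plan) | 91.1% | 94.9% |
| 3 kg | 91.1% | 93.8% |
| 0 kg | 91.0% | 91.2% |

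**Step 5. Error rates.** With all arms equal, the chance of at least one false claim is about 4.7–4.8% under both rules. With one effect large and the other null, the false-claim rate on the null comparison is 2.5% under the fixed rule and 5.0% under Holm. With IP–EUC at the planned 6 kg and GP = IP, it is 2.5% and 4.9%. Holm stays within 5% up to simulation error in every case run.

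**The case against.** The strongest objection is that a prespecified Bonferroni split is legitimate, GP–IP already exceeds 90%, and the fixed rule caps each comparison's false-positive rate at 2.5% whatever the other shows. If IP beats EUC but GP equals IP, Holm nearly doubles the chance of wrongly declaring GP superior. That is true and belongs among the costs. It does not make the fixed rule better at the error rate the plan appears to have chosen: two tests at 2.5% imply a 5% family-wise budget, and Holm spends that budget without exceeding it. A team that wants 2.5% for each comparison in its own right could keep the fixed rule, but the plan does not say this is the aim.

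It is also fair that the 83% to 89% gain concerns the completers analysis, while the primary analysis is intent-to-treat with multiple imputation, and that fixed 97.5% intervals are simple to match to the tests.

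A reader might infer two stronger points that the documents do not support:

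- **That the plan pays for multiplicity twice**, with an F-test gate and then a split alpha. The text puts the ANOVA first but never makes its significance a condition. Even as a gate it would cost nothing under the planning means, where F-test power exceeds 99%. The whole gain comes from replacing the fixed split with a step-down rule.
- **That an F-test at 0.05 followed by t-tests at 0.05 is an equally good replacement.** With three arms it does control family-wise error (4.3% for the two named contrasts with all arms equal, 5.0% with one effect real). But it can lose rejections that an ungated 0.025 rule makes. With assumed losses of EUC 6, IP 4 and GP 8 kg, GP–IP power falls from about 91% to about 90%. Only Holm rejects everything the fixed rule rejects.

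**Conclusion.** The point holds as a matter of efficiency. The fixed 0.025 rule controls error, agrees with the power calculation and has correctly stated powers, so nothing in the plan is invalid. Holm gives about 4 percentage points more power for GP–IP with the full sample, about 6 with 20% loss, and about 5 points (8 with loss) for winning both comparisons.

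These figures rest on the plan's assumptions: 2, 8 and 12 kg, a common SD of 7 kg, independent observations and two-sided t-tests. The GP–IP gain is conditional on IP–EUC being significant and nearly vanishes if IP and EUC do not differ. Label: cheap improvement.

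**What to change.** In the Analysis plan paragraph, replace the fixed 0.025 threshold with Holm's procedure on IP–EUC and GP–IP: the smaller p-value is tested at 0.025 and, only if it is significant, the other at 0.05. State that both tests are two-sided, and that the global ANOVA is reported descriptively and is not a condition for the pairwise tests. Holm needs only the two p-values that the imputation analysis already yields. Keep the stated powers as the conservative case.

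The cost is one or two sentences, made before unblinding, with no extra participants. The downsides to accept are the false-positive rate of up to 5% on one comparison when the other effect is real, and simultaneous confidence intervals that no longer match the tests in a simple way. The 97.5% intervals can still be reported alongside.
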